#### 9.5 Target Population:

Describe the population to whom the study findings will be generalized

The target population is DoD service members, DoD beneficiaries, and Veteran Affairs beneficiaries, 18-55 years of age, evaluated and treated at William Beaumont Army Medical Center (WBAMC) Emergency Department (ED) El Paso, Texas with a diagnosis of acute musculoskeletal pain.

#### 9.6 Benefit to the DoD:

State how this study will impact or be of benefit to the Department of Defense

It is the primary aim of the study to demonstrate that low dose intramuscular ketorolac, 15 mg, is not inferior to high dose intramuscular ketorolac, 60 mg, for the treatment of musculoskeletal pain. In proving the primary aim of the study, it is our hypothesis that the total man hours lost will decrease as a result of better pain management at the time of presentation to the emergency department. Second, by demonstrating that the lower dose is not inferior, this study may help increase patient satisfaction scores within military emergency departments. Lastly, by providing evidence with this single-blind, non-inferior study, it may be inferred that our results will add to the current set of literature which could become a pathway to building a larger multi-center study.

During his tenure, the previous Chief of Staff for the Army, GEN Mark Miley, clearly maintained that readiness is the priority of the U.S. Army. The military medical community is front and center in maintaining the DoDs level of readiness. This study aims to demonstrate that low dose intramuscular ketorolac is not inferior to high dose intramuscular ketorolac. By demonstrating non-inferiority, it is postulated that patients receiving the lower dose of ketorolac may experience a faster return to work period. This shorter period may equate to less man hours lost. This hypothesis is based on previously demonstrated higher incidents of dose related adverse events.

We anticipate that there will be a lower rate of adverse outcomes by utilizing lower doses of ketorolac. These findings result in multiple benefits to the DoD, service member, and beneficiary. First, by showing a lower rate of adverse outcomes, treating with the lower dose may improve readiness by decreasing lost man hours. Secondly, reducing the amount of adverse effects while maintaining the same level of therapy, patient satisfaction may improve, as well.

## 10.0

### **Study Procedures, Data Management, and Privacy**

#### **10.1 Study Procedures:**

Describe step-by-step how the study will be conducted from beginning to end

##### Definitions

1. Acute – onset of symptoms within 30 days on the day of data collection.
2. Musculoskeletal (MSK) – a general term used to described the various forms of pain effecting the musculoskeletal system, for this study. The types of pain included in this definition are undifferentiated muscular, undifferentiated bony, undifferentiated soft tissue, neck, back (to include cervical, thoracic, lumbar, and sacral), shoulder, arm, elbow, forearm, wrist, hand, hip, thigh, knee, leg, ankle, foot and digits).
3. Potential subject – any patient presenting to the WBAMC ED meeting age inclusion criteria with an Emergency Severity Index (ESI) score of 4 or 5 and having a chief complaint of musculoskeletal (MSK) pain, as defined above.
4. Subject – any potential subject meeting aforementioned criteria for enrollment, who met all inclusion criteria, who did not meet any exclusion criteria, who provided informed consent, and signed the Healthcare Information Portability and Accountability Act (HIPAA) Authorization Form.
5. Subject Study Packet –the packet containing documents used to annotate eligibility, acceptance, and consent to participate in the study. Forms included within the packet are the Ketorolac Research Form, Informed Consent Form, HIPAA Authorization Form, and VAS forms (1-3).

Subject Study Number – The randomized number assigned to each subject in order to de-identify data for purpose of protecting Personal Identifiable Information during the reporting of the study's results.

##### Prescreening / Recruitment Process

During the consent process, the patient will be informed that there is the potential for inadequate pain control while participating in this study. They will be informed that they are entitled to additional pain control medications at any time, as appropriately determined by their provider. See the second to last paragraph of section 5 of the Informed Consent Form. Due to the nature of the study, study subjects requiring additional analgesia prior to the 60-minute re-evaluation will be unenrolled. No further data will be collected once they are unenrolled.

Female potential subjects require a separate further step in order to be officially enrolled as subjects. The following four paragraphs describe the process for enrollment of female subjects. Pregnancy and breast feeding meet exclusion criteria for this study and the following paragraphs describe exactly how investigators will take multiple steps to ensure that only non-pregnant females are enrolled.

As stated above, female potential subjects will be required to provide a urine sample to complete a POC UHCG test. Due to this requirement, their informed consent includes consent to providing a single urine sample for testing. They will be informed that their urine is not required for or used for any other part of the study or data collection.

The POC UHCG is a test performed by WBAMC nurses and it can be performed in triage, usually only taking a few minutes. The result of the POC UHCG is documented by the nurse as positive or negative in the comments section of the T-System™ home screen, indicating either pregnancy or no pregnancy respectively. WBAMC ED uses the QuickVue+® One-Step hCG Combo Test (manufactured by Quidel Corporation). Per manufacturer clinical trials, both the sensitivity and specificity for this test is 99%. Despite the fact that this test is imperfect at detecting pregnancy, it does have a very high sensitivity and specificity. Using this process, investigators are confident that only non-pregnant females will be enrolled in the study.

Specimens collected will not be retained for further use, will be destroyed in accordance with WBAMC lab specimen policy and will not be used for any other purpose unless directed by the attending provider (e.g.: urine culture or urinalysis as ordered by the attending provider).

All POC UHCG results will be communicated with the attending provider (verbally and by being documented in the comments section of the T-System™ home screen) and the attending provider will be responsible for conveying the results to the female potential subject. In the event that the female potential subject is a patient of the PI during the PIs ED shift, the PI with the permission of the attending may also convey the results of the test.

Upon meeting all of the aforementioned criteria for enrollment, providing a signature on the Informed Consent Form and HIPAA Authorization Form, the potential subject will be considered enrolled as a subject for the study.

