3. HIPAA Authorization Form: signature of this document authorizes investigators use of the subject's protected health information (PHI) and personally identifiable information (PII) responsibly, securely and only for the purposes of this study. PHI and PII will be explained in detail to the patient and all questions will be honored. Should the patient decline to sign this document, they will be excluded from the study.
  1. PHI: The only protected health information used for this study will be the (1.) chief complaint and (2.) vital signs. A review of systems (ROS) will be used for inclusion and exclusion purposes of this study, but the EHR will not be accessed for this information and this information will not be documented on any media. A detailed description of the ROS is provided later in this application.
  2. PII: The only PII used for this study will be the (1.) subject name, (2.) age (in years-not date of birth), (3.) medical record number (MRN) and (4.) gender.

4. VAS forms (pretreatment and post-treatment): these are single page forms with a 0-100 mm VAS. Four separate VAS forms will be included in the Subject Study Packet and will be used to assess the subject's pain prior to administration of ketorolac, and at the 30 and 60 minute intervals after ketorolac administration. A fourth form will be included in the event that the patient completes the VAS incorrectly. The subject in each instance and on separate forms, will be asked to mark a horizontal line on the 0-100 mm continuum indicating their pre-treatment level of pain and their pain level post-treatment at the 30 minute and 60 minute intervals. Three separate forms are utilized to control for response bias. The Subject Study Number will also be included on the document, but otherwise no other information will be contained on the VAS forms.

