All appropriate provider and nursing policies, safeguards and regulations governing the preparation and administration of parenteral medication within the WBAMC ED will be followed and standard of care for the injection of ketorolac will not be altered, omitted or deviated from industry, ethical, moral or hospital standards. The investigators will not have any part in preparation or administration of the ketorolac-this will be completely handled by WBAMC ED nursing staff and the order for the ketorolac will have already been approved and prescribed by the WBAMC attending ED provider through the EHR.

As the medication is prepared for administration, the investigator will educate the subject on the use of the VAS and annotate their pre-treatment pain score on the VAS form. For the purposes of this study, the VAS is a validated tool that will be used to objectively measure the subject's response to ketorolac.

The subject will then be injected intramuscularly with the dose of ketorolac randomized to the patient based on the Subject Study Number assigned to the randomized packet, which was assigned to that subject. Again, all appropriate provider and nursing policies, safeguards and regulations governing the preparation and administration of parenteral medication within the WBAMC ED will be followed and standard of care for the injection of ketorolac will not be altered, omitted or deviated from industry, ethical, moral or hospital standards.

Following the administration of ketorolac and at the 30 and 60 minute intervals, VAS scores will be recorded, the patient will be assessed for adverse effects (objective and subjective) and blood pressure and heart rate measurements will be taken. At the conclusion of the 60 minute period and documentation of the VAS and any adverse effects, the data collection phase will be considered complete. The subject will be notified that the study has concluded. The attending provider will then continue with evaluation, treatment, and disposition, as indicated.

As outlined during the consent process, additional analgesia will be available during the course of the study. The decision to provide additional analgesia will be made by the attending provider in consideration of the study subject's clinical scenario. Study subjects who receive additional analgesia will be unenrolled from the study at the time of administration of the additional analgesia.

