### **11.0 Statistical/Data Analysis Plan**

#### **11.1 Statistical Considerations:**

List the statistical methods to be used to address the primary and secondary objectives, specific aims, and/or research hypotheses. Explain how missing data and outliers will be handled in the analysis. The analysis plan should be consistent with the study objectives. Include any sub-group analyses (e.g., gender or age group). Specify statistical methods and variables for each analysis. Describe how confounding variables will be controlled in the data analysis

The primary outcome will be the difference in VAS from baseline to 30 minutes and from baseline to 60 minutes. Our research hypothesis is that the measured pain relief using 15mg of intramuscular ketorolac will be non-inferior to the measured pain relief using 60mg of intramuscular ketorolac. Whereas in a clinical study where the research hypothesis is that one treatment, say drug A, is demonstrated to have a better (improved pain relief) outcome than the second treatment, say drug B, we are hypothesizing that smaller dose drug is not inferior in terms of pain relief than the higher drug dose. We fully suspect that the higher drug dose will have a better average outcome, but the question of interest is, is the outcome for the lower dose drug non-inferior to that of the higher drug dose. The analysis used in this study is a non-inferiority test. This hypothesis can be tested using a variety of methods that involve the construction of one-sided confidence interval or one-sided, two-sample equal-variance t-test with alpha of 0.05. In both methods, the power and sample size can be computed.

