**11.5 Please provide a justification for your sample size**

In this study, we assume that we are comparing the mean VAS between the 2 Groups, and the margin of non-inferiority is -13 mm. The actual difference between the means is assumed to be 0 and the standard deviation is assumed to be 27 for the 2 Groups (estimated from the Motov manuscript). Group sample sizes of 55 and 55 achieve 80% power to detect non-inferiority using a one-sided, two-sample equal-variance t-test with alpha of 0.05. The sample size per arm was increased from 55 to 61 to account for an anticipated 10% dropout or withdrawal of subjects (5.5 subjects was rounded to 6 subjects).

**11.6 Data Analysis Plan: Complete description: Background, Objectives, Design, Step by Step how the project is going to be done, Data analysis plan:**

To test for non-inferiority of dose 15mg to dose 60 mg using the VAS pain score, the analysis to be used is called an interval test. The hypothesis will be tested using the construction of one-sided confidence intervals or one-sided, two-sample equal-variance t-test with alpha of 0.05. To test that the lower dose has less adverse effects, we will use the one-sided z-test for testing two independent proportions. All tests will be conducted at the 0.05 level of significance.

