The ESI is a standardized ED triage algorithm utilized nationwide to stratify patient triage acuity. ESI scores range from 1 to 5, with 1 being the most emergent medical conditions and 5 being the least emergent medical conditions. For an example, a patient with an ESI score of 1 may have severe trauma or present in cardiac arrest, whereas a patient with an ESI score of 5 may only require a medication refill or suture removal. For the purpose of this study, only ESI scores of 4 or 5 will be included. The rationale for excluding ESI categories 1-3 is that ESI categories of 4 and 5 are unlikely to have been the result of, or develop into a serious injury or illness during a patient’s ED stay. ESI categories 1-3 may require extensive laboratory, imaging and/or opiate pharmacotherapy during their ED stay, which may confound study results. Whereas, a patient presenting with an acute MSK injury or pain and an ESI category of 4 or 5 will have a greater likelihood of being treated with a single non-opioid analgesic, such as ketorolac. Therefore, by choosing ESI categories 4 or 5, our study makes it unlikely that the patient has a serious medical process (or that a serious medical issue will develop during their ED stay) and/or will require opiate analgesics during their ED stay. Also, selecting for ESI categories 4 or 5 increases the likelihood of ketorolac being the only analgesic required during their ED stay. A complete explanation of ESI scores is beyond the scope of this document; more information can be obtained at <https://www.ahrq.gov>. Subjects who meet the age inclusion criteria, have an ESI score of 4 or 5 and a chief complaint of MSK pain will be considered prescreened as potential subjects for enrollment in this study.

Note: the primary investigator will be conducting the research during time allocated for research. He will not be a part of the care team for the potential study subjects.

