There is a very low risk for harm with participation in this study as the medication is being administered as recommended by the package insert and as recommended by the Food and Drug Administration. Furthermore, patients who are at increased risk for these adverse events will not be enrolled in the study, based on questions asked using the inclusion and exclusion criteria during the consent process. Ketorolac has the following known adverse events with applicable percent of patients who experience these effects: headache (17%), gastrointestinal pain (13%), dyspepsia (12%), nausea (12%), edema (4%), hypertension, dizziness (7%), drowsiness (6%), diaphoresis, pruritus, skin rash, diarrhea (7%), constipation, flatulence, gastrointestinal fullness, gastrointestinal hemorrhage, gastrointestinal perforation, gastrointestinal ulcer, heartburn, stomatitis, vomiting, anemia, prolonged bleeding time, purpura, increased liver enzymes, pain at injection site (2%), tinnitus, and renal function abnormality.

Additionally, there is a risk that the study subjects receiving the 15 mg dose will have inadequate pain control.

There is also the risk of accidental disclosure of protected health information (PHI) or personally identifiable information (PII). However, name and MRN will only be listed on the Master Key. The remainder of the research data will only have the Study Subject Number.

There are specific risks to pregnant and breastfeeding women. There is an FDA boxed warning that ketorolac is contraindicated in labor and delivery due to the potential to inhibit uterine contractions and adverse effects on fetal circulation. Additionally, ketorolac has a pregnancy risk factor of C. In this category, risk to the mother and fetus cannot be ruled out.

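### Dosed subjects who need additional analgesia before 60 minutes leave the study, so the 60-minute non-inferiority test runs on a set selected by outcome; if 15 mg is truly worse, this favours non-inferiority by an amount the documents do not fix

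*Protocol*

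**What the plan says.** The removal rule stands in two places in protocol section 10.1. Under Prescreening / Recruitment Process, "study subjects requiring additional analgesia prior to the 60-minute re-evaluation will be unenrolled. No further data will be collected once they are unenrolled". Under Medication Administration, "Study subjects who receive additional analgesia will be unenrolled from the study at the time of administration of the additional analgesia". The first turns on needing analgesia, the second on being given it.

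The VAS records "pain prior to administration of ketorolac, and at the 30 and 60 minute intervals after ketorolac administration", and at no other time. Section 11.1 makes the change to 30 minutes and the change to 60 minutes the primary outcome. A subject rescued between 30 and 60 minutes therefore has no 60-minute value, and one rescued before 30 minutes has no post-dose value at all.

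On handling, the template prompt in section 11.1 reads "Explain how missing data and outliers will be handled in the analysis", and the answer beneath it is silent on missing data. The SAP names an independent-samples t-test but no analysis set, imputation rule or sensitivity analysis. Section 10.2 (Descriptive Statistics Data) says that data on subjects who need further analgesia serve descriptive purposes only. Section 13.6 has the data of a subject who withdraws destroyed, and mentions withdrawal and exclusion together. It is not clear whether that reaches a subject unenrolled for rescue who already has a 30-minute VAS.

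**The concern.** Needing more analgesia within the hour is itself a sign that the study dose did not work well. Removing those subjects removes poor outcomes from whichever arm has more of them. The protocol gives two reasons to think that this could be the 15 mg arm. Section 11.1 states: "We fully suspect that the higher drug dose will have a better average outcome". Section 14.1 states that "there is a risk that the study subjects receiving the 15 mg dose will have inadequate pain control". If so, the worst 15 mg responses drop out of the 60-minute comparison more often than the worst 60 mg responses, the remaining arms look more alike, and in a non-inferiority trial that is the direction of the conclusion sought.

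The allowance in section 11.5 does not deal with this: "The sample size per arm was increased from 55 to 61 to account for an anticipated 10% dropout or withdrawal of subjects". It restores the number of subjects but does nothing about which subjects are lost.

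**Working it through.** **Convention.** Difference = mean VAS reduction on 15 mg minus that on 60 mg; negative means 15 mg is worse.

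**Inputs from section 11.5.** Margin -13 mm, SD 27, true difference 0, one-sided equal-variance t-test at 0.05, 55 per arm for 80% power, raised to 61. **Not in the documents:** the rescue rate, how closely rescue follows relief, and the true deficit. These are assumed below.

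**Step 1: the plan's own figure.** SE = 27 × √(2/55) = 5.149, and 13/5.149 = 2.525. The noncentral t gives 80.6% power at 55 per arm and 79.98% at 54, so 55 is reproduced. The allowance is 55 × 1.10 = 60.5, rounded to 61.

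**Step 2: where the test turns.** t(0.95, 108 df) = 1.659, and 1.659 × 5.149 = 8.54. With 55 per arm and an observed SD of 27, the test passes when the observed difference is above -13 + 8.54 = -4.46 mm. A shift of about 1 mm decides only results close to that line.

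**Step 3: arithmetic without a rescue model.** If m15 and m60 of 61 subjects per arm are removed, and those removed are k mm worse than those kept, the shift is k × (m15 - m60)/61. Assume 12 of 122 are lost and the true deficit is 13 mm, where the test should wrongly pass 5% of the time.
- Split 7/5, k = 10: 10 × 2/61 = 0.33 mm; false non-inferiority 5.7%.
- Split 9/3, k = 20: 20 × 6/61 = 1.97 mm; false non-inferiority 10.3%.

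**Step 4: rescue fully determined by relief.** Let relief have mean 0 on 60 mg and -13 on 15 mg, with SD 27, and let everyone below a common cut be rescued. For 5% rescue on 60 mg the cut is 27 × (-1.645) = -44.4. Rescue on 15 mg is then Φ((-44.4 + 13)/27) = 12.2%. The mean of those kept is 2.93 on 60 mg and -6.76 on 15 mg, so the observed deficit is 2.93 + 6.76 = 9.69 mm instead of 13. With 1% and 10% rescue on 60 mg, rescue on 15 mg is 3.3% and 21.2%, and the observed deficit is 11.7 and 8.3 mm. With a true difference of 0 both arms are cut alike and the difference stays 0.

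**Step 5: simulation with partly random rescue.** 61 per arm, 20,000 trials per cell, true deficit 13 mm, rescued subjects dropped. ρ is the assumed correlation between poor relief and rescue. Entries are false non-inferiority for completers at 60 minutes.

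| Overall rescue | ρ = 0 | 0.3 | 0.5 | 0.7 | 1 |
|---|---|---|---|---|---|
| 2% | 5.0% | 5.3% | 6.0% | 6.4% | 8.5% |
| 5% | 4.8% | 5.4% | 6.6% | 8.0% | 13.0% |
| 10% | 5.1% | 5.5% | 7.2% | 10.2% | 20.8% |

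At 10% rescue the mean estimated deficit falls from 13.0 mm (ρ = 0) to 9.3 mm (ρ = 1). With a true difference of 0 it stayed within 0.1 mm of 0 in every cell.

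**Step 6: VAS bounded at 0 and 100, completers against a pre-rescue value.** Assumed: baseline mean 65 and SD 18; 60 mg reductions of 20 mm at 30 minutes and 25 mm at 60; correlation 0.7; 15 mg shortfall of 8 or 13 mm at 30 minutes and 13 mm at 60; rescue by chance among subjects with a high 30-minute VAS or a small 30-minute reduction. The 30-minute VAS stands in for the pre-rescue mark.

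| Overall rescue | Completers | Pre-rescue value used |
|---|---|---|
| 2% | 4.8-5.6% | 4.6-5.2% |
| 5% | 4.8-6.6% | 4.2-5.5% |
| 10% | 4.8-8.3% | 3.5-6.0% |

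If instead the 10% with the least 30-minute reduction are the ones rescued, completers give 9.1% (30-minute shortfall 8) and 12.9% (shortfall 13), and the pre-rescue value over-corrects, to as low as 2.9%. Carrying the baseline VAS forward gave 6.4-7.6% against 4.8-7.4% for completers and was no better in any of 8 scenarios.

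Steps 2 to 6 concern the 60-minute test. The 30-minute comparison is affected only by rescue before 30 minutes.

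**The case against.** The other side has four good arguments.

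First, the direction depends on a true deficit. Section 9.2 reports an analgesic ceiling of 10 mg, below both study doses, and an emergency-department trial of intravenous ketorolac with similar relief at 10, 15 and 30 mg. Section 11.5 plans on a true difference of 0. At 0, with rescue decided alike in both arms, nothing shifts. This stands, and it makes the concern conditional. It does not remove it, because a non-inferiority test exists to guard against the case where the lower dose is worse.

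Second, rescue may be rare. Section 13.3 says that "selecting for ESI categories 4 or 5 increases the likelihood of ketorolac being the only analgesic required during their ED stay". This also stands. At 2% rescue most scenarios lie near the nominal 5%.

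Third, the plan is not wholly silent: unenrolment together with descriptive-only use points to exclusion from inference. That is fair. The accurate complaint is that exclusion is implied but not defined, and that as implied it selects on outcome.

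Fourth, the pre-rescue value is imperfect. In one mild scenario of step 6 (30-minute shortfall 8 mm, 10% rescue) false non-inferiority was 5.5% for completers and 6.0% with the pre-rescue value, because a value from 30 minutes understates a deficit that widens by 60. This belongs among the stated costs.

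A reader might go further and infer that the plan tilts the trial toward 15 mg whatever the truth, or that its error rate is 21%. The documents support neither. The first fails at a true difference of 0. The second needs 10% rescue, a 13 mm deficit and rescue fully determined by relief, none of which the documents state.

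**Conclusion.** The concern holds in conditional form and should be fixed. As written, randomised and dosed subjects leave the 60-minute primary comparison because of an event that reflects the outcome, and no defined analysis set brings them back. If 15 mg is truly worse and rescue follows poor relief, the estimate moves toward non-inferiority.

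The size is unknown. The percentages above are illustrations at a true deficit equal to the margin, not bounds. They run from no inflation, when rescue is unrelated to relief or very rare, to the extreme cases in step 5. The sample size of 55 per arm is not in error on this point.

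**What to change.** In both places in protocol section 10.1, and in the SAP:

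- Keep all randomised, dosed subjects in their assigned arm in the primary analysis set.
- Record one VAS mark immediately before any additional analgesia and use that post-dose, pre-rescue value for later time points. If there is none, or collection has already ended, use a 30-minute VAS taken before rescue where it was retained. Do not carry the baseline VAS forward.
- For subjects with no post-dose VAS, report the number by arm and show the result over a range of assumed values, for example 0, 13 and 26 mm worse than the rest of the 15 mg arm.
- Present completers as a sensitivity analysis, and report all post-randomisation removals by arm.
- State that unenrolment for rescue is not withdrawal of consent, so data already collected are kept. Reconcile the two rules in section 10.1 (requiring against receiving) with section 10.2 (Descriptive Statistics Data) and section 13.6.

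When and how additional analgesia is given does not change.

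**Cost.** Protocol, SAP and matching consent wording, and one extra VAS form per packet. Section 10.1 lists three VAS forms in places, and the fourth that it mentions is reserved for a form completed incorrectly. The estimate may be less favourable to 15 mg, and the pre-rescue value can over- or under-correct, including slightly more false non-inferiority than completers if the deficit widens between 30 and 60 minutes. At a true difference of 0 and 10% rescue, simulated power is 80-83%, against 81-83% for completers. In the range analysis it is 80-81% with unobserved 15 mg subjects set 13 mm worse, and about 76% with them set 26 mm worse.
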